### **5.4 Subject Enrollment/ Randomization and Blinding/ Subject Replacement**

Subjects in Stage 1 will be enrolled to receive the combination everolimus with escalating doses of RX-0201. Subjects in Stage 2 will no longer be randomized to 1 of 2 treatment arms (i.e., everolimus versus everolimus/RX-0201). All subjects in Stage 2 will now be assigned to the everolimus/ RX-0201 treatment arm. Subjects in Stage 1 who are enrolled but not treated and subjects who discontinue treatment before completion of Cycle 1 for reasons other than the occurrence of a DLT may be

replaced. Any replacement subject will be enrolled into the same dosing cohort as that for the subject who withdrew.

Subjects in Stage 2 who are enrolled but not treated will be replaced.

## 5.5 Study Variables

### 5.5.1 Definition of Dose-Limiting Toxicity

Reference should be made to the CTCAE, Version 4.03 for grading of the severity of adverse events and laboratory abnormalities. Dose-limiting toxicities (DLT) will be evaluated during Cycle 1 of treatment. These DLTs will be graded and documented according the National Cancer Institute Common Terminology Criteria for Adverse Event (NCI CTCAE) (v4.03) A DLT will be defined as the occurrence of any of the following that are determined by the investigator to be related to RX-0201:

- Grade 4 neutropenia ( $ANC < 0.5 \times 10^9/L$ ) with fever or lasting 3 days or longer
- Any Grade 4 thrombocytopenia or Grade 3 thrombocytopenia associated with  $\geq$  Grade 1 hemorrhage
- Any  $\geq$  Grade 3 coagulation abnormality (defined by PT and/or INR and PTT values) associated with clinical hemorrhage  $\geq$  Grade 1.
- Nausea/vomiting  $\geq$  Grade 3 despite maximal antiemetic therapy; diarrhea  $\geq$  Grade 3 despite maximal anti-diarrheal therapy.
- Grade 4 thrombocytopenia (platelet count  $< 25 \times 10^9/L$ )
- Any other non-hematological toxicity  $\geq$  Grade 3 with the exception of alopecia

### 5.5.2 Dose Escalation and Definition of Maximum Tolerated Dose

Initially 3 subjects will be enrolled to receive everolimus plus 125 mg/m^2/day of RX-0201. Depending on whether there are any dose limiting toxicities (DLTs) attributed to RX-0201, the following dose-escalation decisions and rules will be followed:

#### Dose-escalation decisions:

Dose Group	Theoretical dose (mg/m  /da)	Escalation
1	125	-
2	200	1.60
3	250	1.25

#### Dose-escalation rules:

- If 0 of the first 3 subjects experience DLT during the first 3 weeks of treatment, then the dose will be escalated to the next higher level in 3 subsequent subjects.
- If 1 of the first 3 subjects experiences DLT at the current dose during the first 3 weeks of treatment, then 3 more subjects will be accrued at the same dose level.
- If 0 of the 3 additional subjects experience DLT during the first 3 weeks of treatment, then the dose will be escalated to the next higher level in 3 subsequent subjects.
- If  $\geq 1$  of the 3 additional subjects in a cohort experiences DLT in the first 3 weeks of treatment, the MTD has been exceeded and 3 more subjects will be treated at the next lower dose level (if only 3 subjects were previously treated at that prior dose level).
- If  $\geq 2$  of 3 or  $\geq 2$  of 6 subjects experience DLT during the first 3 weeks of treatment, then the MTD has been exceeded and 3 more subjects will be treated at the next lower dose level (if only 3 subjects were previously treated at that prior dose level).
- Each group of 3 subjects within a cohort must be observed for a minimum period of 3 weeks without DLT before subsequent subjects are enrolled at the next higher dose level.
- Escalation to the next dose level of the study can occur upon review of the safety data from all ongoing and previous subjects and with the concurrence of the study sponsor and the principal investigators.

In the event that attribution of causality of potential DLTs to study agent may be equivocal, discussions with the safety review committee will occur and additional subjects may be enrolled at that dose level. The decision to escalate to the next dose level will be based upon observation of DLTs during Cycle 1 from at least 3 subjects in the previous dose level. Reviews will be conducted by the safety review committee to monitor safety data on an ongoing basis throughout the study. In addition, the investigators and/or the Medical Monitor may prompt a meeting by the safety review committee at any time. Rexahn or its designee will notify the sites when enrollment into a dose level is complete and when the next dose level is open to enrollment during Stage 1.

### 5.5.3 Determination of MTD or the RX-0201 Recommended Stage 2 Starting Dose

The establishment of the MTD or the safety of the target RX-0201 dose of 250 mg/m^2/day will be based on a review of the overall safety data by the safety review committee. The MTD is the highest starting dose level associated with first-cycle DLTs in < 33.3% of subjects. Once the safety of the MTD of the target RX-0201 dose of 250 mg/m^2/day is initially established, additional subjects (up to 20 subjects total) will be enrolled to receive the target RX-0201 dose of 250 mg/m^2/day in Stage 2. Selection of a recommended Stage 2 starting dose from within the tested dose ranges and schedules will be based on evaluation of available safety information with findings regarding compliance, and achievement of targeted pharmacokinetic values.

## **6 Sample Size**

Sample size calculation for this study has been empirically set. Approximately 32 subjects will be recruited and enrolled into the study over 20 centers in the US.

For Stage 1, approximately 9 subjects will be enrolled in to receive the combination of everolimus (10 mg) and RX-0201 at increasing doses of RX-0201 to the MTD or up to a target dose of 250 mg/m^2/day. For Stage 2, approximately 3 additional subjects will be treated with everolimus alone arm and up to 20 subjects in the everolimus/RX-0201.

## **7 General Considerations**

The software used for all summary statistics and statistical analyses will be SAS Version 9.4 or later.

Safety, Efficacy, and PK assessments will be summarized separately for Stage 1 and Stage 2.

Additional summaries and analyses of pooled Phase 1 and 2 data may also be generated based on applicability of dosing regimens.

Unless otherwise noted, data will be summarized in tabular format by increasing dose level of RX-0201 for the combination of RX-0201 and Everolimus in Stage 1, by combination of RX-0201 and Everolimus in Stage 2, and by RX-0201 dose level for the combination of RX-0201 and Everolimus Stage 2. All groups combined (i.e., Total/Overall column) will also be presented when appropriate. All study data documented on the eCRFs will be included in the study data listings.

### **7.1 Timing of Analyses**

Analysis window is not defined in this study.

### **7.2 Analysis Population**

#### **7.2.1 Full Analysis Set**

The Full Analysis set includes all enrolled subjects with subjects analyzed according to the treatment assigned at enrollment/randomization. All efficacy endpoints will be analyzed using the Full Analysis set.

#### **7.2.2 Per Protocol Analysis Set**

The Per-Protocol Analysis set includes all subjects without pre-specified major protocol deviations. Sensitivity analyses of some efficacy endpoints may be performed using the per-protocol analysis set.

### **7.2.3 Safety Analysis Set**

The safety analysis set includes all subjects who receive at least one dose of study drug(s) with subjects analyzed according to the treatment received. All safety data will be analyzed in accordance with this analysis set. The safety analysis set will be defined as all subjects who receive at least 1 dose of study drug. These subjects will be analyzed according to the treatment received. All safety data will be analyzed in the safety analysis set.

### **7.2.4 Dose Limiting Toxicity Analysis Set**

The dose limiting toxicity assessment set will include all evaluable subjects. An evaluable subject is any subject who experiences a dose limiting toxicity in the first 21 days of treatment or completes 2 weeks of RX-0201 treatment in cycle 1.

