5.4 Subject Replacement

Subjects in Stage 1 who are enrolled but not treated and subjects who discontinue treatment before completion of Cycle 1 for reasons other than the occurrence of a DLT may be replaced. Any replacement subject will be enrolled into the same dosing group as that for the subject who withdrew.

Subjects in Stage 2 who are enrolled but not treated will be replaced.

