6.3 RX-0201 Dose Limiting Toxicity

Initially 3 subjects will be enrolled to receive everolimus plus 125 mg/m²/day of RX-0201. If there are any dose limiting toxicities (DLTs) attributed to RX-0201 the following dose-escalation decisions will be followed:

Table 1: Phase 1 RX-0201 Dose Escalation		
Dose Group	Theoretical dose(mg/m²/day)	Escalation
1	125	-
2	200	1.60
3	250	1.25

The following dose-escalation rules will be employed:

- If 0 of the first 3 subjects experience DLT during the first 3 weeks of treatment, then the dose will be escalated to the next higher level in 3 subsequent subjects.
- If 1 of the first 3 subjects experiences DLT at the current dose during the first 3 weeks of treatment, then 3 more subjects will be accrued at the same dose level.
- If 0 of the 3 additional subjects experience DLT during the first 3 weeks of treatment, then the dose will be escalated to the next higher level in 3 subsequent subjects.
- If ≥ 1 of the 3 additional subjects in a cohort experiences DLT in the first 3 weeks of treatment, the MTD has been exceeded and 3 more subjects will be treated at the next lower dose level (if only 3 subjects were previously treated at that prior dose level).
- If ≥ 2 of 3 or ≥ 2 of 6 subjects experience DLT during the first 3 weeks of treatment, then the MTD has been exceeded and 3 more subjects will be treated at the next lower dose level (if only 3 subjects were previously treated at that prior dose level).
- Each group of 3 subjects within a cohort must be observed for a minimum period of 3 weeks without DLT before subsequent subjects are enrolled at the next higher dose level.
- Escalation to the next dose level of the study can occur upon review of the safety data from all ongoing and previous subjects and with the concurrence of the study sponsor and the principal investigators.

In the event that attribution of causality of potential DLTs to study drug may be equivocal, discussions with the investigators, medical monitor and sponsor will occur and additional subjects may be enrolled at that dose level. Reviews will be conducted by the investigators, medical monitor and sponsor of all available safety data on an ongoing basis throughout the study. The study sponsor or its designee will notify the sites when enrollment into a dose level is complete and when the next dose level is open to enrollment during Stage 1.

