6.4 Determination of MTD or the RX-0201 Recommended Stage 2 Starting Dose

The establishment of the MTD or the safety of the target RX-0201 dose of 250 mg/m²/day will be based on a review of the overall safety data by the investigators, medical monitor and sponsor. The MTD is the highest starting dose level associated with first-cycle DLTs in < 33.3% of subjects. Once the safety of the MTD of the target RX-0201 dose of 250 mg/m²/day is initially established, additional subjects (up to 20 subjects total) will be enrolled to receive the target RX-0201 dose of 250 mg/m²/day in Stage 2. Selection of a recommended Stage 2 starting dose

from within the tested dose range will be based on evaluation of available safety information with findings regarding compliance, and achievement of targeted pharmacokinetic values.

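### SAP 7.2.4 counts DLTs over 21 days but requires no follow-up to Day 21 from a DLT-free subject, so a subject lost in the third week can enter the Stage 1 DLT denominator as a non-event

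*SAP*

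**What the plan says.** SAP 7.2.4 gives two routes into the DLT set. A subject is evaluable who "experiences a dose limiting toxicity in the first 21 days of treatment or completes 2 weeks of RX-0201 treatment in cycle 1". The first route is for a subject with an event, the second for a subject without one. Nothing is said about observation after the infusion ends.

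The other sections use the full cycle:

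- SAP 5.5.1: "Dose-limiting toxicities (DLT) will be evaluated during Cycle 1 of treatment".
- SAP 5.5.2, first escalation rule: "If 0 of the first 3 subjects experience DLT during the first 3 weeks of treatment", the next level opens.
- Protocol 6.3: each group of three "must be observed for a minimum period of 3 weeks without DLT" before the next level is enrolled.
- Protocol 6.4: "The MTD is the highest starting dose level associated with first-cycle DLTs in < 33.3% of subjects".

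On leavers, Protocol 5.4 says that in Stage 1 "subjects who discontinue treatment before completion of Cycle 1 for reasons other than the occurrence of a DLT may be replaced". SAP 5.4 repeats this.

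**The concern.** The two routes are not symmetric. A DLT on Day 18 makes a subject evaluable and is counted. A subject who disappears on Day 18 without a recorded DLT is also evaluable and is counted as DLT-free, although part of the third week was never seen. Any error therefore lowers the DLT rate and never raises it.

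DLT incidence is the Stage 1 primary endpoint (SAP 4.2) and is still to be tabulated by dose (SAP section 8, Safety Analyses). The cohorts have three or four subjects, so one subject wrongly scored as a non-event is a large share of the denominator.

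**Working it through.** **Reference figures.** SAP 7.2.4 gives no number of its own. The Stage 1 plan around it is coherent: 3 dose levels × 3 subjects = 9, as stated in Protocol 9.3; Protocol 2.3.2 reports 3 + 4 + 3 = 10 treated. The MTD threshold agrees with the escalation rules: 1/6 = 16.7% passes, and 2/6 = 33.3% fails.

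**Length of the gap.** The window is 21 days and the requirement for a DLT-free subject is 14 days, so 21 − 14 = 7 days, or 7/21 = 33% of the window, can be unobserved.

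**Who can fall into it.**

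| Situation after 14 days of RX-0201, no DLT so far | Planned follow-up | In the set under SAP 7.2.4? |
|---|---|---|
| Stays on study | Through Cycle 1 | Yes, correctly |
| Stops treatment only | End-of-treatment visit with laboratory tests (Protocol 6.9, 7.8); safety visit 30 (+7) days after last dose (Protocol 7.9) | Yes, correctly, if those visits happen |
| Lost, or withdraws consent for follow-up, before Day 21 | None assured | Yes, as a non-event |

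Only the last row is a problem. Replacement under Protocol 5.4 is optional and does not take the replaced subject out of the set.

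**Why the third week carries information.** In Protocol Appendix A, Stage 1 hematology, chemistry and coagulation are scheduled at screening, Cycle 1 Day 1, Day 1 of later cycles, and the end-of-treatment or early-termination visit. The Day 2, 8, 15 and 16 procedures (Protocol 7.3.5 and 7.3.7 to 7.3.9) list none. Four of the six DLT criteria in Protocol 6.5 depend on neutrophil, platelet or coagulation values. A subject lost after Day 14 without an early-termination visit can therefore be scored DLT-free with no scheduled post-dose safety laboratory result.

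**Which denominator.** Protocol 9.5.2.1 links the DLT summary to a DLT assessment set, which Protocol 9.2.2 does not define. SAP 7.2.3 sends all safety data to the safety set. SAP 8.1 lists four analysis sets and omits the DLT set. If the safety set were used, subjects with even less follow-up would enter, so the problem remains either way.

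**Size, by illustration.** The documents do not give the timing of DLT risk. Assume a constant hazard over 21 days, and one of three subjects seen only to Day 14. For a true 21-day rate p, the chance of seeing that subject's DLT is q = 1 − (1 − p)^(14/21), and the expected observed rate is (2p + q)/3.

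- p = 1/3: q = 1 − (2/3)^(2/3) = 0.237; (0.667 + 0.237)/3 = 30.1% instead of 33.3%.
- p = 0.20: q = 1 − 0.8^(2/3) = 0.138; (0.400 + 0.138)/3 = 17.9% instead of 20.0%.

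If instead 50% to 80% of the risk falls in Days 1 to 14, q = 0.5p to 0.8p. For p = 1/3 the expected rate is then (0.667 + 0.167)/3 = 27.8% to (0.667 + 0.267)/3 = 31.1%.

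With zero recorded DLTs the reported rate is 0% whatever the denominator. What changes is the apparent precision: the one-sided 95% upper limit is 1 − 0.05^(1/3) = 63.2% with three subjects and 1 − 0.05^(1/4) = 52.7% with four. The plan does not ask for this limit; it only shows how much one counted subject is worth.

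**The case against.** The strongest reply is that stopping treatment is not stopping observation. Protocol 6.9, 7.8 and 7.9 plan an end-of-treatment visit with full laboratory tests and a safety visit about a month after the last dose, unless consent for follow-up is withdrawn. Two weeks is also the whole RX-0201 course of a cycle, so it is a sensible exposure criterion, and a DLT must be related to RX-0201. A subject who completes the course, stops everolimus and is followed contributes valid data, even if a replacement is also enrolled. All of this stands, and it limits the gap to subjects lost or withdrawing from follow-up before Day 21. It does not close the gap, because SAP 7.2.4 does not require that any of those visits took place.

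Two stronger readings are tempting and are not supported.

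- *That the rule distorted escalation or the choice of the Stage 2 dose.* Escalation was governed by the separate three-week observation rule (Protocol 6.3, SAP 5.5.2). Protocol 2.3.2 reports Stage 1 complete and the dose declared in the amendment of March 2017, before the 2018 SAP revisions.
- *That the fourth subject at 200 mg/m²/day was such a leaver, turning 1/3 = 33.3% into 1/4 = 25% and so crossing the MTD threshold.* One DLT in the first three would have required three more subjects at that dose, making six. Four subjects followed by escalation to 250 mg/m²/day fits no DLT in the first three. A fourth subject could equally have replaced someone who stopped before Day 14, whom SAP 7.2.4 already excludes.

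**Conclusion.** The definition is inconsistent with the DLT window used throughout both documents and should be corrected, but the point is small and concerns reporting only. SAP 7.2.4 allows a subject with up to 7 of 21 days unobserved to count as DLT-free. The resulting bias can only be downward: about 3 percentage points for one such subject in three at a true rate of 33.3% (30.1% under constant hazard; 27.8% to 31.1% over the assumed range). These sizes rest on an assumed timing of risk and on an assumed subject. The documents do not show that anyone was lost between Day 14 and Day 21. If nobody was, the table is unaffected. If no DLT was recorded, the rate reads 0% either way and only the number of subjects behind it changes.

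**What to change.** In SAP 7.2.4, define an evaluable subject as one with a DLT in Days 1 to 21, or one who completed the Cycle 1 RX-0201 course and was followed for DLTs through Day 21, with the already scheduled end-of-cycle or end-of-treatment/early-termination safety laboratory tests available.

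In addition:

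- Name this set as the denominator of the DLT table, reconciling Protocol 9.5.2.1 with SAP 7.2.3, and add it to the sets counted in SAP 8.1.
- List, by dose, every Stage 1 subject who was replaced or whose DLT follow-up was incomplete, with the last day observed.

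This is an analysis definition. It needs no new data collection and no change to treatment or escalation rules. The cost is one clause, one denominator statement and one listing. The downside is at most a slightly smaller denominator; there is no change if all subjects were followed to Day 21.

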### **7.2.5 Pharmacokinetic Analysis Set**

The pharmacokinetic analysis set will include all enrolled subjects who undergo blood sampling during the study and have measurable concentrations of RX-0201 above the respective assays' limit of quantification at any time point after dosing. Evaluable for Tumor Response Analysis Set (Stage 2 only)

The analysis of objective response includes all subjects in the Full Analysis Set (and per-protocol set if applicable) with a uni-dimensional measurable lesion at baseline (as per RECIST 1.1 with modifications).

### **7.2.6 Missing Data**

In general, data will be analyzed as received from the clinical database. Hence, except for some partial/missing dates (see below), missing values, including those caused by dropouts, will not be imputed. Missing or partially missing dates in the following situations will be imputed for purposes of analysis:

### **7.2.7 Partial/Missing Dates for Study-Related Visits or Procedures**

It is anticipated that all study-related visit and procedure dates entered into the clinical study database will be complete (i.e. day, month, year are all recorded) and accurate. Any missing or partially missing

dates of this type will be queried before statistical analyses are performed. If the day, month, and/or year are still unknown, then the dates will be imputed as follows for purposes of analysis:

- If the day of the visit or procedure date is missing, then take the previous visit and add the target number of days to the next visit according to the visit schedule.
- If the month of the visit or procedure date is missing then take the previous visit and add the target number of months to the next visit according to the visit schedule.
- If the year of the visit or procedure date is missing, then the year will be queried. If the year is unknown, no imputation of year will take place.

Imputed dates will be flagged in the subject data listings.

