6.1.2 RX-0201 Dosing Schedule

RX-0201 will be administered on a cyclical basis. For subjects assigned to receive RX-0201 and everolimus, a cycle will be defined as the period elapsing from the first day of RX-0201 administration through Day 21 of the cycle or to the recovery from any adverse events sufficient that a new cycle of therapy can be administered (e.g., on Day 29 or Day 36), whichever occurs later. Once a new cycle starts, the prior cycle is considered to be completed. For subjects assigned to the everolimus only arm, a cycle will be defined as the period elapsing from the first day of everolimus administration through Day 21 of the cycle or to the recovery from any adverse events sufficient that a new cycle of therapy can be administered, whichever occurs later.

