### **7.2.8 Partial/Missing Dates for Adverse Events**

For any adverse event that has a missing or incomplete start date, a query will be issued to capture the full date. If only a partial date is reported for the start of an AE, a complete date will be estimated using the following algorithm:

- If only the year is reported (i.e., missing the month and day): The date of the first dose of investigational product will be used as the start of the AE.
- The year and month are reported (i.e., missing the day): The first day of the month will be imputed.
- The month and day are reported (i.e., missing the year): only situations where the year is self-evident will be allowed.

No imputation will be applied to an incomplete AE end date. The rationale will be that there should be a start date for all subject AEs but there may not be an end dates for AEs that are ongoing at the time the subject exits the study.

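### SAP 7.2.7 and 7.2.8 do not require an imputed date to agree with the recorded month or year; the effect is small, falls mainly on AE timing, and is cheap to remove

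*SAP*

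**What the plan says.** SAP 7.2.7 covers visit and procedure dates. It expects them to be complete, and partial ones are handled first by query: "dates of this type will be queried before statistical analyses are performed". For dates that remain partial it has three rules.

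- Day missing: "then take the previous visit and add the target number of days to the next visit according to the visit schedule".
- Month missing: "then take the previous visit and add the target number of months to the next visit according to the visit schedule".
- Year missing: "If the year is unknown, no imputation of year will take place".

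Imputed visit and procedure dates are flagged in the listings.

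SAP 7.2.8 covers AE start dates, again after a query. If only the year is known, "The date of the first dose of investigational product will be used as the start of the AE". If the year and month are known, the first of that month is used. This section says nothing about flagging.

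These dates feed later analyses. PFS events and censoring are dated by tumour assessments (SAP 4.3 and the censoring table in SAP 9.1.1). Treatment-emergent status depends on onset relative to the start of study drug (Protocol 9.5.2.1, SAP 8.10). Safety analyses are also run by cycle and week where appropriate (the Safety Analyses text after SAP 8.6).

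**The concern.** A sound imputation rule fills in the missing part of a date and leaves the known part alone. The AE rule for a known month and year does this. The other rules set no such condition.

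- **Day-missing rule.** It builds the date from the schedule and never checks it against the recorded month.
- **Month-missing rule.** It needs a target in months, but the visit schedule is written in days and 21-day cycles (Protocol Appendices A and B), so no such target exists.
- **Year-only AE rule.** It does not compare the reported year with the year of first dose. It also refers to the investigational product, and Protocol Section 6 says RX-0201 is the only one, so the roughly 3 everolimus-alone subjects have no date to impute.
- **Previous visit.** The SAP does not say whether this means the last clinic visit or, for a scan, the last scan. Two programmers could derive different dates.

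At stake are the cycle and week of some AEs, the treatment-emergent status of a few pre-dose AEs, and occasionally a scan date used for PFS.

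**Working it through.** The plan states no figure here, so there is none to reproduce. The rules are applied literally; all calendar dates below are assumed.

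1. **Year-only AE, later year.** First dose 15 Nov 2017, AE year 2018. The rule gives 15 Nov 2017. The earliest date the record allows is 1 Jan 2018, 47 days later; the latest, 31 Dec 2018, is 411 days later. On 1 Jan 2018 the subject is nominally in cycle floor(47/21) + 1 = 3, but the AE is tabulated in Cycle 1. It is treatment-emergent either way.

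2. **Year-only AE, earlier year.** First dose 10 Jan 2018, AE year 2017. Onset was at least 10 days before dosing (31 Dec 2017 to 10 Jan 2018). The rule gives 10 Jan 2018, so the AE can be counted as treatment-emergent. The opening is narrow. Screening lasts up to 14 days and dosing should follow within 5 days of enrolment (Protocol 7.2, 5.3), so first dose must fall in about the first 14 + 5 = 19 days of January. With uniform start dates that is 19/365.25 = 5% of subjects.

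3. **Day 1 visit after a delayed cycle.** The next Day 1 is nominally Day 22. Protocol 6.1.2 lets a cycle run on ("e.g., on Day 29 or Day 36), whichever occurs later"). The imputed date is early by 29 − 22 = 7 or 36 − 22 = 14 days. Example: Day 15 visit on 20 June, Day 1 recorded as July with the day unknown. The rule gives 20 June + 7 = 27 June, outside the recorded month; the true date is 4 or 11 July.

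4. **Scan, previous visit read as the last clinic visit.** Stage 2 imaging is on Days 18–21, after the Day 15 visit of the same cycle (Protocol 7.6, Appendix B). The target is therefore Day 15 plus 3 to 6 days, and for a scan done in its window the error is at most 6 − 3 = 3 days. It can still cross a month end: Day 15 on 28 May gives 31 May to 3 June.

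5. **Off-schedule scan.** First dose 2 Jan 2017, Cycle 6 Day 15 on 10 May 2017, progression scan recorded as June 2017. The rule gives 13–16 May, 131–134 days after first dose (4.30–4.40 months). Any June date gives 150–179 days (4.93–5.88 months). The landmark is 4.5 × 365.25/12 = 137 days, so the event changes sides. This needs a scan at least 22 days after Day 15 (Day 37 or later), well outside the window.

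6. **Scan, previous visit read as the last scan.** The end-of-Cycle-6 scan is nominally on study days 5 × 21 + 18 = 123 to 6 × 21 = 126. One 14-day delay since the last scan moves a Day 126 scan to Day 140, while the rule still returns Day 126. The landmark lies between them.

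7. **Weight of one event.** Without earlier censoring, one event moved across the landmark shifts the Kaplan-Meier estimate by 1/20 = 5 percentage points in the combination arm (20 subjects).

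**The case against.** The best defence is that these rules will rarely be used. Dates are queried first. Scans are kept as source documents (Protocol 7) and must be reviewed before the next cycle (Protocol 7.6), so a scan date still partial after query is unlikely. The SAP also does not say that recorded parts are discarded; it is silent, and a careful programmer might keep them. All of this stands as a limit on size. It does not supply the missing condition, and flagging in listings does not correct an estimate.

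Three stronger readings are tempting, and the documents do not support them.

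- **That cycle delays make PFS systematically early.** A delay comes after Day 21 and moves the next Day 1. The scan is dated from Day 15 of its own cycle, which already carries earlier delays. The link to PFS holds only for off-schedule scans or if the previous visit means the previous scan.
- **That DLT counts are distorted, because an AE can be moved into Cycle 1.** DLTs are identified directly in the EDC (SAP 4.3), and Stage 1 was complete with its dose declared (Protocol 2.3.2) before the current SAP version was written.
- **That wrong AE years are common, because treatment plus follow-up often spans a New Year.** Spanning a New Year is not the same as an AE starting after it, many subjects stop early, and the rule applies only when the month and day are both unknown after query.

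**Conclusion.** The rules as written can give dates that the record contradicts, and two parts cannot be applied at all: the month-missing rule, and the year-only AE rule for everolimus-alone subjects. This is a minor point.

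- **AEs.** A later-year event lands in the wrong cycle and week, but incidence is unchanged. An earlier-year event can wrongly become treatment-emergent, in a small share of subjects.
- **Visits.** A Day 1 visit after a delayed cycle is 7 to 14 days early.
- **Scans.** The error is normally a few days. It is larger only in the two situations described in working steps 5 and 6, where a single event could cross the 4.5-month landmark.

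The conclusion rests on a literal reading of the two sections. The documents do not say how many partial dates are expected after query; I assume few. The 5% figure assumes uniform start dates.

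**What to change.** Amend SAP 7.2.7 and 7.2.8 before database lock:

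- State that imputation never changes a recorded day, month or year.
- Define the previous visit, and say which visit anchors a scan date.
- Day missing: use the schedule-based date only if it falls in the recorded month; otherwise use the nearest day in that month. In working step 3 this gives 1 July, and in step 5 it gives 1 June, on the correct side of the landmark.
- Month missing: replace the rule in months with the schedule in days, restricted to dates consistent with the recorded parts. Simply leaving such dates missing would leave some PFS events or censoring times undated.
- Year-only AEs: use first dose of any study treatment only if it falls in the reported year; use 1 January of the reported year if that year is later; treat the AE as pre-treatment if it is earlier.
- Flag imputed AE dates in the listings, as is already done for visits.

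The cost is a few sentences and a few lines of code, with no change to design or data collection.
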